NYSPI 7944

V.12222022

NCT04249596

Tianeptine for Treatment Resistant Depression

1. Introduction

Major depressive disorder (MDD) is a leading cause of disability in adults worldwide (~16M patients in US alone). Unfortunately, only ~40% of patients achieve full remission following first-line treatment with a selective serotonin reuptake inhibitor (SSRI), creating a pressing need for new therapeutic approaches to address treatment-resistant depression. One strategy for improving treatment response recognizes the potential for underlying mechanistic heterogeneity in MDD and the associated need for focused treatments targeting biologically distinct subgroups of MDD patients. Significant evidence suggests dysfunction of endogenous opioid signaling pathways as a key biological deficit in some MDD patients. Before the advent of electroconvulsive therapy and tricyclic antidepressants in the 1950s, the administration of opioid receptor agonists was unsystematically used for treatment of depression. Several case studies and small clinical trials have pointed to the efficacy of opioid agonists in treating MDD, with some limited evidence in treatment-resistant patients as well. Relatedly, deficiencies in physical and emotional pain modulation observed in depressed patients are likely to be linked with underlying dysfunction in endogenous opioid signaling. Patients with MDD report physical pain symptoms more than twice as often as non-depressed individuals¹⁻³, chronic pain is a significant risk factor for developing depression⁴, and the presence of comorbid pain is a negative prognostic factor for antidepressant treatment⁵. Functional magnetic resonance imaging (fMRI) studies suggest that physical pain and social rejection activate common brain regions, such as the dorsal anterior cingulate cortex (dACC) and anterior insula (aINS)^{6,7}. Moreover, emotional pain resulting from adverse social experiences (e.g., childhood abuse and neglect, romantic rejections, etc.) increases vulnerability to depression^{8,9}, and reduced pleasure from social interactions contributes to withdrawal, reduced social support, and the persistence of a depressive episode once it develops¹⁰.

We hypothesize that a subgroup of MDD patients with deficient opioid receptor signaling will better respond to pharmacological interventions specifically targeting this biological mechanism. Studies from our laboratories show that endogenous opioids act at the mu-opioid receptor (MOR) in response to social rejection and that this response is dramatically blunted in depressed individuals.¹¹ In addition, preliminary data from our lab show that healthy individuals with high trait rejection sensitivity (RS) also show reduced MOR activation, similar to depressed individuals. Notably, approximately one third of all patients with MDD have a “long-standing pattern of interpersonal rejection sensitivity”¹²⁻¹⁴, a common feature in, although not restricted to, the “atypical” subtype of MDD¹⁵⁻¹⁷. Thus, high RS may represent the behavioral manifestation of

underlying deficits in endogenous opioid signaling and blunting of opioid release observed in some depressed patients in response to social rejection.¹¹ Indeed, our recent fMRI study showed that women with MDD display exaggerated emotional and neural responses to social rejection, particularly in the right anterior insula.¹⁸ In response to social acceptance, women with MDD responded with positive emotions, however neural activity in the nucleus accumbens, a reward structure, was dissociated from subjective happiness.¹⁸ Since MOR regulates social distress and social reward in animals^{19–28} and humans^{11,29}, interventions targeting this mechanism may be *more effective than conventional treatments in treating high RS MDD* by regulating the neural pathways activated during social rejection and social acceptance.

In this application, we propose to target MOR signaling in depressed patients with tianeptine. Tianeptine is an atypical antidepressant that has been used clinically in Europe, Asia, and South America since the late 1980s in millions of patients.^{30–34} Its efficacy in humans is well documented, and comparable to, or better, than that of several commonly used classes of antidepressants, including selective serotonin reuptake inhibitors (SSRIs) and tricyclic antidepressants (TCAs).^{30–40} However, tianeptine's molecular mechanism of action had remained unknown until recently. Work in our laboratories has shown that tianeptine acts as a selective agonist of MOR, signaling in a manner analogous to enkephalins and endorphins, the endogenous opioid peptides.^{41,42} Using both genetic knockout and pharmacological inhibition in mouse models for the study of depression, we have collected strong evidence that MOR is the direct molecular target by which tianeptine exerts its antidepressant effects, an entirely unique mechanism among existing antidepressants. Importantly, at clinical doses, tianeptine does not produce euphoria; in fact, at 6 times the normal dose, patients reported no euphoria.⁴³ Furthermore, unlike treatment of pain by traditional opioid agonists, prolonged occupancy of the receptor is not required for the antidepressant effect. Instead, much like the hypothesized pulsatile and time-limited action of endogenous opioids in response to social rejection and acceptance, tianeptine-induced MOR agonism sets in place a signaling cascade that leads to lasting physical changes in dendritic structure in key brain circuits.^{44,45} Of note, tianeptine was never approved for clinical use in the US, but has been used safely and widely throughout Europe, Asia, and South America for decades.

The major goals of this project are (1) to define the relationship between opioid signaling deficits and response to tianeptine treatment, (2) to develop a comprehensive assessment battery capable of identifying endogenous opioid signaling deficits to explore biological heterogeneity in the MDD population, and (3) ultimately to improve the response rate compared to standard of care in a subgroup of MDD patients selected based on biomarkers of opioid signaling deficiencies.

References

We have chosen to recruit subjects and perform all assessments except for neuroimaging procedures at the two sites (N=24 at each site for overall study N=75, 28 already entered), which will increase the rate of participant enrollment, ensure that recruitment goals are met, and enhance the generalizability of the sample. Structural and task-based magnetic resonance imaging (MRI) will be performed solely under [name] direction at NYSPI in order to maintain internal validity of the data set. MSSM subjects will be transported to NYSPI to complete neuroimaging procedures as described below.

2.2. Subject recruitment and screening procedures.

Recruitment will proceed in parallel at each study site by means of (1) screening individuals who directly contact the clinical programs at MSSM and SUSM, (2) referral from clinicians in other disciplines at the component institutions participating in this project, and (3) outreach to the communities surrounding MSSM and SUSM. We also promote recruitment of under represented minority subjects by anticipating and working to eliminate barriers to research participation. Promotional materials at each component clinic allay these concerns by explaining how our studies are designed to mitigate and overcome these barriers to participation in research studies.

Potential subjects will be evaluated by remote and/or in-person meetings. Those who decide to participate by signing informed consent will have an evaluation inclusive of a clinical interview by a study clinician, structured diagnostic interview, and completion of standardized rating scales (trained rater) in order to document eligibility. Eligible subjects will have further documentation of vital signs, medical history urine drug screen, CBC, chemistries and electrolytes, thyroid profile, urine analysis, standing/supine systolic/diastolic BP, and ECG. Female participants will undergo urine pregnancy testing to confirm that they are not pregnant prior to drug initiation and will be instructed to use effective birth control during the study, such as condoms, IUDs, oral contraceptives, or depot contraceptives. Participants also will be scheduled for further baseline testing as described below.

2.3. Imaging procedures.

Pre- and post-treatment brain MRI for subjects enrolled at MSSM will be performed on each subject using a 3T Siemens Prisma scanner located at NYSPPI. Participants from the MSSM site will have transportation arranged and paid at the study's expense. Subjects will be compensated for their time spent in transit in addition to regular compensation for MRI procedures.

At the start of the scanning session, a 3-Plane localizer (scout) will be acquired to determine patient position. Subjects will then receive (1) T1-weighted 3D for volumetric analysis and coregistration of functional MRI data, (2) EPI scan during Thermal pain sensitivity task, (3) EPI scan during Social Feedback task, and (4) EPI scan while Resting. For the MRI procedures, participants are instructed to lie as still as possible within the magnet. The MRI scan is completed in one session lasting for a total of 60 minutes. All precautions and protections are given to the participant to ensure that they are as safe and as comfortable as possible. The participant is given a squeeze ball to terminate the scan at any time. Conducting these procedures will be an accredited Magnetic Resonance Technologist and one member of the research staff (Bachelor's Level or Higher).

MRI data will be analyzed with Statistical Parametric Mapping (SPM). We will conduct a whole-brain analysis in a voxel-by-voxel brain-wide search as well as hypothesis-driven region of interest (ROI) analysis (Bonferroni-corrected alphas for multiple VOIs) to examine brain areas (e.g., amygdala, nucleus accumbens, ventrolateral prefrontal cortex, anterior cingulate cortex, anterior insula) previously shown to regulate responses to physical pain as well as positive and negative social stimuli. Statistical parametric maps are obtained using whole-brain image subtraction routines with the images warped to standardized space.

Thermal Pain Sensitivity Task: Thermal stimulations will be delivered to left volar forearm using an MRI-safe delivery system. Series of 10 second stimuli will be administered, each followed by an 18-22 seconds rest period. We will administer series of moderately painful temperatures (one subjectively rated as level 6 on a 0-10 VAS scale and one standard temperature of 45°) in a semi-random order (random for participant, same order across subjects). With a calibration procedure performed before the MRI,¹ we will choose the temperature to administer in fMRI on a participant-by-participant basis to be sure that the subjective pain intensity is constant across participants. During the task itself, participants are asked to stare at a fixation cross during each trial and focus on the sensations elicited by the somatic stimulus. Participants are then instructed how to rate their after each trial using ten-point VAS scales . In the

second part of pain task, instead of resting between pain stimuli participants are asked to interact with other by playing a computer ball-tossing game.

Social feedback task: Prior to the scanning session, all subjects will complete an “online profile” (e.g., gender, age, birthdate, race/ethnicity, orientation, major/occupation, hobbies, personal qualities, years of education, etc.) and provide a digital photo of her/himself prior to rating profiles of others. If subjects do not have a photo available or prefer, they may have a digital photo taken during the interview. All subjects then complete online ratings of personal profiles from a collection of over 500 men and women with whom they would be most interested in forming a close personal relationship. Subjects will be informed that this task is a simulation, and that others’ ratings of the subject are not “real.” During the scanning session, subjects are presented with their own picture along with a picture of a highly rated profile, along with feedback that they were liked (acceptance trial), not liked (rejection trial), or that others were undecided or had not yet rated them (neutral trial). Questionnaires will be given before, during, and/or after the task to assess cognitive and emotional states. For questionnaires, answer choices are presented on Likert scale (e.g., 5 discrete choices), or a visual analogue scale (e.g., a sliding scale), verbally, on paper, or on a computer.

2.4. Comprehensive assessment of physical and emotional pain functioning.

The hypothesis under investigation in this study is that a subgroup of depressed outpatients experience brain opioid signaling dysfunction, which manifests behaviorally as increased physical and emotional pain sensitivity, and will be predictive of greater response to tianeptine (i.e., due to its mu-opioid receptor agonism). In addition to the imaging procedures described above, this hypothesis will be further studied by having participants complete a assessment battery testing pain functioning at baseline and study endpoint, in addition to further weekly assessments of selected measures.

All subjects will complete the baseline evaluation, which includes psychiatric assessments (HARS, STAI, IDS-SR, CGI, MMSE), physical pain tests (Thermal Sensitivity Test, BPI, Physical and Psychological Pain Scale), as well as emotional pain and interpersonal wellbeing tests (ARSQ, C-SSRS, Psychache scale, Perceived Stress Reactivity Scale (PSRS), Perceived Stress Scale, Shyness and Sociability Scale, Reaction to Implied Rejection Measure, Hurt Feelings Questionnaire, Multidimensional Scale of Perceived Social Support)

2.5. Summary of visit schedule and other study assessments.

As described above, at Screening, patients who decide to participate by signing informed consent will undergo a psychiatric clinical interview, and eligibility is determined by assessments with the Structured Clinical Interview Diagnostic for DSM 5 (SCID) and 24-item Hamilton Rating Scale for Depression (HRSD). Eligible subjects will complete screening laboratory tests and those currently taking other antidepressant medications will be tapered off under the supervision of the research staff according to standard clinical practice or by the doctor currently prescribing the medication. There will be a 5 day wash-out period from the time the previous antidepressant has been stopped before tianeptine is started, 3 weeks if the previous antidepressant was a monoamine oxidase inhibitor and 4 weeks if the antidepressant was fluoxetine. For participants requiring an antidepressant taper, the screening psychiatric assessments will be repeated post-

taper to confirm inclusion criteria are still met. Eligible subjects will then complete the remainder of the baseline evaluation, which includes the Hamilton Anxiety Rating Scale (HARS), State Trait Anxiety Inventory (STAI), Inventory of Depressive Symptomatology—Self Report (IDS-SR), Clinical Global Impressions (CGI) Severity and Improvement, Mini Mental State Examination (MMSE), physical pain tests (BPI), emotional pain tests (ARSQ, C-SSRS, Psychache scale), Drug Abuse Screen Test (DAST), and Michigan Alcohol Screen Test (MAST). Finally, for patients who are willing to participate, whole-blood samples will be drawn and used to screen for genetic polymorphisms in the genes for the mu-opioid receptor (e.g., A118→G), oxytocin receptor, vasopressin receptor 1A, and monoamine oxidase A, all of which have been shown to moderate behavioral and neural responses to rejection. Blood samples will be stored for future analysis if other potential genetic biomarkers are later identified.

Following screening and baseline measures, subjects will undergo MRI scanning, which is performed prior to Week 0. At Week 0, tianeptine medication will be initiated at 12.5 mg po tid. The first dose of tianeptine 12.5 mg is given at the Week 0 appointment under the supervision of study staff so that initial response can be observed. Subjects will be instructed not to consume any food for at least 3 hours prior to their appointment to control any food effect on tianeptine's pharmacokinetics. Orthostatic blood pressure and heart rate will be measured before tianeptine administration, subjects will be observed for a period of 1 hour.

Subjects return at Weeks 1, 2, 3, 4, 5, 6, 7, and 8 (+/- 2 days) for depression follow-up visits and complete the HRSD, CGI Severity and Improvement, IDS-SR, and Structured Pill Count Interview. At baseline, week 4 and week 8 subjects will also repeat the following tests: HARS, VAS Physical and Psychological Pain Scale. Perceived Stress Reactivity Scale (PSRS), Perceived Stress Scale Psychache Scale, UCLA Loneliness Scale, Shyness and Sociability. Reaction to Implied Rejection Measure. Hurt Feelings Questionnaire. Adult Rejection Sensitivity Questionnaire, Multidimensional Scale of Perceived Social Support, Brief Pain Inventory (BPI).. All baseline measures will be repeated at study endpoint (Week 8), including a post-treatment MRI scanning visit at NYSPI.

Revised table of procedures and timetable is shown below:

Procedures and Assessments	Timepoints									
	Screening	Baseline w0	w1	w2	w3	w4	w5	w6	w7	End of Tx w8
Informed Consent	x									
Inclusion/Exclusion	x									
Vital Signs ^a	x	x				x				x
ECG	x	x*								x
Clinical Labs ^b	x					x				x
Liver Function Test	x					x				x
Blood Genomics	x**					x**				x**
Urine Pregnancy Test ^c	x	x								x
Urinalysis	x									
Drug Screening	x									
MRI Eligibility Screener	x	x								x
Facial Recognition Task (csv)		x								x
Thermal Calibration (csv)		x								x
Imagery Training, fMRI instructions, practice		x								x
Localizer/Structural MRI/Field Map		x								x
Social Feedback Task (csv)		x								x
Resting State		x								x
Thermal Pain Task (csv)		x								x
Visual Analogue Scale-Body Pain		x								x
Social Feedback Follow-Up		x								x
Study Medication Dispensation		x	x	x	x	x	x	x	x	x
Demographics/Profile Ratings	x	x								
Taper Antidepressant Medication ^d	x									
ATHF	x									
Medical History	x									
SCID	x									
MMSE	x									
Clinical/Medication Progress Note	x	x	x	x	x	x	x	x	x	x
Pill Count			x	x	x	x	x	x	x	x
AE Assessment		x	x	x	x	x	x	x	x	x
HRSD 24-item	x	x	x	x	x	x	x	x	x	x
HARS		x				x				x
CGI S/I	x	x	x	x	x	x	x	x	x	x
CSSR-S		x								x
Social Feedback Profiles rating		x								x
IDS-SR		x	x	x	x	x	x	x	x	x
VAS Physical and Psychological Pain Scale		x		x		x		x		x
Perceived Stress Reactivity Scale (PSRS)		x				x				x
Perceived Stress Scale		x				x				x
Psychache Scale		x				x				x
UCLA Loneliness Scale		x				x				x
Shyness and Sociability		x				x				x
Reaction to Implied Rejection Measure		x				x				x
Hurt Feelings Questionnaire		x				x				x
Adult Rejection Sensitivity Questionnaire		x				x				x
Multidimensional Scale of Perceived Social Support		x				x				x
BPI (pain)		x				x				x
PBI (parent bonding)		x								
Childhood Trauma Questionnaire		x								
Faces Discrimination Task		x								x
MRI scan (structural, SFT, Resting State, Pain Task)		x								x

^a Vital signs include blood pressure and pulse

^b Clinical labs include CBC, Chem 7, TSH, Cholesterol, B12, and Folate

^c Pregnancy test will be performed on women of child bearing potential

^d Washout period only for subjects on other antidepressant medication

* Assessment may be repeated based on clinician discretion; ** Optional

2.6. Tianeptine administration.

Following screening and baseline testing, all subjects will begin tianeptine 12.5 mg three times daily (total daily dose 37.5 mg/day) for a total duration of 8 weeks of treatment. Subjects who develop side effects that prevent them from taking the full three times daily dosage will have their dosage reduced to tianeptine 12.5 mg twice daily, and those unable to tolerate at least 25 mg/day dosing will be dropped out of the study. Based on the extensive experience of clinicians in Europe, where tianeptine is approved for the treatment of depression, we expect this dosage regime to be well-tolerated. During the study, concomitant use of other antidepressants, antipsychotics, anticonvulsants, central nervous system stimulants, anti-addiction agents, and cognitive enhancers are prohibited, with the exception of small doses of benzodiazepines (≤ 2 mg lorazepam equivalents per day), which will be permitted for anxiety or insomnia.

Medication was purchased from Neuraxpharm in Germany and shipped to the NYSPI pharmacy where it is stored. Medication is shipped to the MSSM pharmacy, where it is packaged and prescribed for MSSSM patients in containers containing a 2 week supply (50 blister packed 12.5 mg pills – enough for two weeks plus an additional pills alloatted in case of a delayed visit) at the 0, 2,4, and 6 week visits and 20 blister packed pills for the final taper. Medication is shipped to the Stanford Depression Research Clinic in the same quantities and it is dispensed to patients using the same procedures as atMSSM. At each in person visit, the subject should return the bottle, and the number of remaining pills will be counted and recorded to monitor compliance.

2.7. Early discontinuation criteria and handling of emergencies.

The risk of non-response to tianeptine during the study period is addressed by having close clinical follow up of study subjects and stringent withdrawal criteria. These criteria are (1) participant withdraws his or her consent; (2) significant clinical worsening in the judgment of the study clinician; (3) a CGI-Improvement rating⁷ by the study clinician of 6 (worse) or 7 (much worse) for 2 consecutive visits; or (4) development of significant side effects or an adverse event grade 3 or higher. Any subject meeting any of these criteria will be withdrawn from the study and treated clinically. Furthermore, subjects may be withdrawn if they repeatedly miss scheduled appointments. If clinical worsening necessitates more intensive treatment, appropriate clinical care will be given but if possible the patient will still complete the ongoing assessments and final imaging visits.

Should a subject express suicidal ideation at any time during a study visit, the study clinician will be contacted immediately to assess the subject and to determine the appropriate course of action. Options for addressing suicidal ideation will include contacting the individual's mental health caregiver (if available), referring for urgent (same day) evaluation and treatment in an outpatient clinic, or emergency room evaluation and hospitalization. Similar practices will be used for other emergencies, including but not limited to psychosis, homicidal or violent thoughts, or an acute change in a subject's physical status.

2.8. Tianeptine taper and post-protocol treatment.

Once all study assessments are completed, subjects will be tapered off of tianeptine medication. Subjects will have their dosage reduced to 12.5 mg twice daily for two weeks, then 12.5 mg once daily for two weeks, and then tianeptine will be discontinued. Subjects will be assessed every two weeks in this post-protocol phase, with continuation of HRSD and CGI rating

scales. Appropriate clinical options will be discussed with any subject demonstrating worsening HRSD (≥ 16 on 24-item scale) or CGI (Improvement score ≥ 5 or Severity score ≥ 4 for two consecutive weeks) scores, most likely including initiation of FDA-approved antidepressant medication.

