3.2 Exclusion Criteria

- 1) Any history of opioid-use disorder

- 2) Any history of moderate- non-opioid (except for Nicotine) substance-use disorder.
- 3) Any severity of alcohol use disorder (including mild)
- 4) Past or current psychosis, psychotic disorder (including psychotic MDD), mania, or bipolar disorder
- 5) Hamilton Rating Scale for Depression (HRSD) suicide item > 2 or Clinical Global Impressions (CGI)-Severity score of 7 at baseline
- 6) Previous or current treatment with Tianeptine
- 7) Current treatment or currently taking an opioid.
- 8) Failed depression treatment with electroconvulsive therapy.
- 9) Acute, severe, or unstable medical illness
- 10) Weight > 300 lbs, or girth size incompatible with scanner bore.
- 11) Any physical or intellectual disability adversely affecting ability to complete assessments. MMSE <26
- 12) for MSSM site - Having contraindication to MRI scanning (such as metal in body) or inability to tolerate the scanning procedures (e.g., severe obesity, claustrophobia)
- 13) Current pregnancy or currently breast feeding.
- 14) Abnormal baseline liver function tests
- 15) Currently being treated with an antidepressant medication, an antipsychotic or mood stabilizer.
 - a) If a participant is taking a protocol dis-allowed medication at the time of screening and despite medication treatment still meets the inclusion criteria of an HRSD>16, the participant may discontinue the medication under the supervision of their treating physician or the study clinician.
- 16) Positive urine toxicity at screening (except for cannabinoid)

4. Primary Study Endpoints

- 1. HRSD change from Week 0 to Week 8

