Unexpected adverse event or *unexpected suspected adverse reaction*. An adverse event or suspected adverse reaction is considered "unexpected" if it is not listed in the investigator brochure or is not listed at the specificity or severity that has been observed; or, if an investigator brochure is not required or available, is not consistent with the risk information described in the general investigational plan or elsewhere in the current application, as amended. For example, under this definition, hepatic necrosis would be unexpected (by virtue of greater severity) if the investigator brochure referred only to elevated hepatic enzymes or hepatitis. Similarly, cerebral thromboembolism and cerebral vasculitis would be unexpected (by virtue of greater specificity) if the investigator brochure listed only cerebral vascular accidents. "Unexpected," as used in this definition, also refers to adverse events or suspected adverse reactions that are mentioned in the investigator brochure as occurring with a class of drugs or as anticipated from the pharmacological properties of the drug, but are not specifically mentioned as occurring with the particular drug under investigation.

Adverse Event Reporting Period: The study period during which adverse events must be reported is normally defined as the period from the initiation of any study procedures to the end of the study treatment followup. For this study, the study drug follow-up is defined as 24 hours following the last administration of study drug (or the end of the study for those who must stop tianeptine but continue with the assessments).

Preexisting Condition: A preexisting condition is one that is present at the start of the study. A preexisting condition will be recorded as an adverse event if the frequency, intensity, or the character of the condition worsens during the study period.

General Physical Examination Findings: At screening, any clinically significant abnormality will be documented. At the end of the study, any new clinically significant findings/abnormalities that meet the definition of an adverse event will also be recorded and documented as an adverse event.

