6.2 Recording of Adverse Events

At each contact with the subject, the investigator will seek information on adverse events (AEs) by specific questioning and, as appropriate, by examination. Information on all adverse events will be recorded immediately in the source document. All clearly related signs, symptoms, and abnormal

diagnostic procedures results will be recorded in the source document. All adverse events occurring during the study period will be recorded. The clinical course of each event will be followed until resolution, stabilization, or until it has been determined that the study treatment or participation is not the cause. Serious adverse events that are still ongoing at the end of the study period will be followed up to determine the final outcome.

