6.5 Stopping Rules

Refer to Section 2.7

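### The on-study prohibited-drug list in 2.6 leaves out opioids, which exclusion 7 bars at entry, and does not say whether it covers the tianeptine taper

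*Combined protocol and SAP*

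**What the plan says.** **After entry.** Section 2.6 states: "During the study, concomitant use of other antidepressants, antipsychotics, anticonvulsants, central nervous system stimulants, anti-addiction agents, and cognitive enhancers are prohibited". It then allows benzodiazepines up to 2 mg lorazepam equivalents a day. Six classes are named, and opioids are not among them.

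**At entry.** Exclusion 7 in section 3.2 is "Current treatment or currently taking an opioid". Exclusions 1 and 16 cover a history of opioid-use disorder and a positive urine toxicology at screening. Exclusion 15a refers to a "protocol dis-allowed medication" being taken at screening, but does not list which drugs that means. In the section 2.5 table, both the eligibility row and the drug-screening row are marked at Screening only.

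**Withdrawal.** Section 2.7 lists four criteria: withdrawn consent, clinical worsening, a poor CGI-Improvement rating at two consecutive visits, and "development of significant side effects or an adverse event grade 3 or higher". Section 6.5 says only "Refer to Section 2.7".

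**Taper.** Section 2.8 steps the dose down over two two-week periods. It adds: "Subjects will be assessed every two weeks in this post-protocol phase". For adverse events, section 6.1 says "study drug follow-up is defined as 24 hours following the last administration of study drug".

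**Pharmacology and risk.** Section 6.4 calls tianeptine a full agonist at the mu-opioid receptor. It cites five overdose deaths, one of them with tramadol also present.

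**The concern.** The protocol will not enrol a patient who is already taking an opioid, but the list that governs the treatment period does not carry that restriction forward. A new opioid prescription during the study is foreseeable: section 1 notes that patients with MDD report physical pain symptoms more than twice as often as people without depression, and dental work or an injury could prompt one at any time.

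At stake is the safety of a patient who takes an opioid analgesic on top of a mu-opioid agonist. The mitigations in section 6.4 (exclusions by history, limited dispensing, collection of unused pills, compliance checks) are aimed at misuse of tianeptine and do not address a second opioid prescribed by someone else. A secondary stake is consistency: two sites that learn of the same kind of uneventful co-use could handle it differently.

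**Working it through.** There is no plan figure to reproduce. The point turns on how the sections fit together, with one short calculation on the taper.

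1. **Is an opioid analgesic in any class named in 2.6?** The nearest class is anti-addiction agents. That plausibly covers opioids used to treat addiction, but not tramadol or another analgesic given for pain.

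2. **Does exclusion 7 carry over?** It is listed as an entry exclusion, and eligibility is checked at Screening. Exclusion 15 is a useful comparison: it bars current antidepressants and antipsychotics at entry, and 2.6 names both classes again for the study period. The protocol therefore restates entry bans when it wants them to continue. The opioid ban is not restated.

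3. **Does exclusion 15a close the gap?** No. It concerns drugs being taken at screening and gives no list of its own.

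4. **Does any other section prohibit opioids on study?** None does. Section 2.7 has no trigger for opioid use, but it has none for the six prohibited classes either. Section 6.5 adds nothing to 2.7.

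5. **Would use come to light?** Possibly. Weeks 0 to 8 give 9 scheduled contacts, and a 4-week taper seen every two weeks gives 4 / 2 = 2 more, 11 in all. Under section 6.2, at each contact "the investigator will seek information on adverse events (AEs) by specific questioning". No section says what follows if a patient reports opioid use without harm.

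6. **How long is the period?**
   - By 2.8: 8 + 2 + 2 = 12 weeks on tianeptine (84 days).
   - Pills that 2.8 requires for the taper: 2 × 14 + 1 × 14 = 42.
   - Pills that 2.6 supplies for the taper: 20, a shortfall of 42 − 20 = 22. At two a day they last 20 / 2 = 10 days, giving 56 + 10 = 66 days on drug.
   - The two sections disagree, so 12 weeks is the length by 2.8 rather than a settled figure. On either reading, tianeptine continues past Week 8.

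7. **Does 2.6 apply in that tail?** Its list holds during the study, while 2.8 labels the taper post-protocol. Section 6.1 keeps adverse-event reporting open until 24 hours after the last dose, so safety follow-up clearly includes the taper. Whether the drug list does is not stated.

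**The case against.** The strongest reply is that harm is already covered. Worsening in the clinician's judgment, significant side effects or a grade 3 event lead to withdrawal under 2.7. The same section has an emergency provision for acute physical change, and the DSMB reviews serious events on an expedited basis. This largely stands: a reader might infer that clinicians are left with no instruction at all, and that is too strong. What lacks a rule is co-use that has not yet caused harm, which is when a rule prevents most.

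A second reply is that exclusion 7 can be read as continuing, since it falls under a heading that covers both selection and withdrawal. Some sites may read it so. But the comparison with exclusion 15 points the other way, and a safety restriction should not depend on which reading a site adopts.

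A third reply is that the missing trigger in 2.7 is not about opioids. That is correct. A reader might infer that 2.7 singles opioids out for neglect, but a patient who starts a banned antidepressant meets no 2.7 criterion either.

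A fourth reply is that the risk evidence is thin. That also stands. The tramadol death is one of five, with no tianeptine dose given. Another of the five involved alprazolam, a benzodiazepine, and 2.6 deliberately permits low-dose benzodiazepines. Section 6.4 also reports only transient effects at 337.5 mg in healthy volunteers, and reversal of overdose with naloxone. The case for change rests on the protocol's own entry ban, not on that death.

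Finally, consent pages, the product label and the manual of procedures are not available here and may say more. The finding is limited to the protocol text.

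**Conclusion.** The gap is real but modest: a cheap improvement for patient safety. The list in 2.6 omits a class that the protocol bars at entry and that shares the study drug's receptor, and the list's reach into the taper is unclear.

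Three stronger conclusions might be drawn, and the documents support none of them:

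- **That co-use at 37.5 mg/day carries a known level of danger.** One co-ingestion death without a stated dose cannot establish that.
- **That the primary HRSD result is compromised.** No rate of on-study opioid use is given, so no bias can be calculated, and nothing here calls for a change to section 5.2.
- **That exposure is firmly 12 weeks.** That is the schedule in 2.8, and the pill supply in 2.6 does not match it.

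The conclusion assumes that 2.6 is read as an exhaustive list and exclusion 7 as an entry criterion. If a site reads exclusion 7 as continuing, the proposed wording simply makes that reading explicit.

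**What to change.** In 2.6:

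- Add to the prohibited classes: *opioids, including tramadol and other opioid analgesics*.
- Add: *This list applies from Week 0 through the last dose of tianeptine, including the taper in 2.8.* Tying the end to the last dose makes the rule work whatever the taper's actual length.
- Add: *Any disclosed opioid use prompts same-day review by the study clinician, who decides whether to stop the opioid or to hold or taper tianeptine.*

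I would leave the action to the clinician and not require discontinuation. After a single dose following dental work, for example, stopping the opioid may be enough.

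The cost is a few lines of text. No visit, laboratory test or analysis is added, and the sample size is unaffected. The downside is at most an occasional interruption or discontinuation of tianeptine.
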